6	July 8 - 2016	Expanded definition of onset of shock to include ANY vasopressors Replaced two AE tables regarding adverse events based on changes in vital signs/laboratory values assessed as unanticipated in the setting of septic shock, as we do not collect sufficient data to produce these tables. Modified tables presented. The analysis of other vasopressors has been split into several components. Sensitivity analyses added to ICU-free days and ICU length of stay. Fluid balance/Urinary output analyses updated Terlipressin added to list of vasopressors for derivation of primary endpoint etc. Definition of primary endpoint imputation for patients lost to follow-up is extended to include any type of withdrawal before Day 30. List of critical adverse events updated (same as before, just re-grouped). No AE tables on AEs leading to withdrawal, as it is not an option to withdraw patient from trial due to AE. Added alternative analysis to "duration of" endpoints, in case normality cannot be assumed for the whole of the data. Small edit in formula in Appendix 5. Continuous version of baseline norepinephrine version is adjusted for weight (categorical version from strata is unadjusted) Added imputation rules for NE and other vasopressors (section 9.4.5) and IMP (section 8.1.1) Appendix 2 slightly updated with corrections. List of protocol deviations modified (section 5)	Version 5

Page 4 of 80

7	Nov 9 - 2017	Additional analyses to MAP analyses. Analysis for duration of septic shock changed from ANCOVA to negative binomial (as blinded data suggests a better fit) with permutation test as backup in case model assumptions do not hold. Analyses for duration of ventilation and duration of RRT changed from ANCOVA to zero inflated negative binomial (as blinded data suggests a better fit) also with permutation test as backup in case model assumptions do not hold. Analysis for ICU length of stay and hospital length of stay changed from ANCOVA to permutation test (as blinded data suggested a non-parametric model). Covariates were dichotomized accordingly. Appendix 4 removed as no longer needed. Appendix 3 updated with variance correction for difference in PVFDs Analyses in 9.4.8, 9.4.9, and 9.4.10 will not be repeated for the selected arm only and data from part 2 only, as they are measured on a subset of patients, probably only in part 1. A "time" by "baseline value" interaction term has been added to the repeated ANCOVA analyses in 9.3.1.5, 9.3.3.1, 9.3.4.1, 9.3.4.2, and 9.4.5 as it is likely that the trajectory over time for each patient will depend on the baseline value. The supportive competing risk and Kaplan-Meier graphs for duration of RRT has been taken out as it makes no sense since RRT durations are short and repetitive. It is more meaningful to just look at 90 day mortality. For the remaining 'duration' endpoints withdrawal rates has been added to the competing risk and Kaplan-Meier graphs. As this is a superiority trial, the PP analysis will only be performed for the primary endpoint, and hence not performed for secondary as previously stated.	Version 6

Date: 20 Nov 2017 E-Statistical Analysis Plan-17877; Ver.9.0 Supersedes: Ver. 8.0 Page 5 of 80

		Only major protocol deviations will be listed. Adverse events graphs added to output. Fluid balance analyses updated. Analyses for norepinephrine/noradrenaline and other vasopressor doses updated. Forest plots added for incidence of RRT (section 9.3.1.8) and mortality (section 9.3.2.3).	
8	Nov 9 - 2017	Format change only. No content was changed	Version 7
9	Nov 20 - 2017	Format change only. No content was changed	Version 8

Page 6 of 80

Signed agreement on Statistical Analysis Plan

TABLE OF CONTENTS

1	Intro	ductionduction	10			
	1.1	Definitions/ Abbreviations	10			
		1.1.1 Definition of Terms	10			
		1.1.2 Abbreviations	10			
2	Trial	Objectives and Endpoints	12			
	2.1	Objectives	12			

		10.4.1 Summary Statistics	
		10.4.2 Data Listings	. 46
	10.5	Episodes of Hypotension	. 46
11	Interin	n analyses	. 47
12	Deviat	ions from protocol analysis	. 48
13	Refere	nces	. 49
14	Tables	, Listings and Figures	. 50
Apper	ndix 1	EQ-5D-5L Quality Adjusted Life Year (QALY)	. 51
Appei		Critical Adverse Events and Classification of Adverse Events Based on Changes in Laboratory Variables	. 52
Appei	ıdix 3	Estimation of Treatment Effects for P&VFDs	. 53
Appei	and Di	Estimation of Treatment Effects for Difference of Proportions in Incidence of RRT, fference in Number of New Organ Failures and Number of New Organ	
	Dysfur	nctions	. 57
Apper	ndix 6	Formal Proof of Type I Error Control	. 69
Appei	ndix 7	Randomisation Plan.	. 74
			. 79

Date: 20 Nov 2017 E-Statistical Analysis Plan-17877; Ver.9.0

Supersedes: Ver. 8.0 Page 10 of 80

1 Introduction

This document describes the planned statistical analyses for selepressin (FE202158) 000133, and is based on protocol dated July 8th 2016 including amendments 1 and 2.

All analyses in the SAP were planned and pre-specified prior to trial termination due to futility.

1.1 Definitions/ Abbreviations

1.1.1 Definition of Terms

Terms Definitions

Evaluable patient Patient who has been treated with IMP and 30 days have passed

since initiation of IMP infusion

Randomised Patient randomised to trial treatment Screened Patient who enters the screening phase

Selepressin FE 202158

Treated patient Randomised and dosed 1-KM curve 1 minus Kaplan Meier curve

1.1.2 Abbreviations

Abbreviations Meanin	g ot	ab	brevia	tions	in	document
-----------------------------	------	----	--------	-------	----	----------

AE Adverse Event

ANCOVA Analysis of covariance
AUC Area Under the Curve
CVP Central venous pressure
EVLW Extra-vascular lung water

EQ-5D-5L EuroQol – 5 Dimensions – 5 Levels

FAS Full-Analysis Set ICU Intensive care unit

IMP Investigational Medicinal Product

ITT Intention-to-treat

LOCF Last observation carried forward

MAP Mean Arterial Pressure

MedDRA Medical Dictionary for Regulatory Activities

NE Norepinephrine
PK Pharmacokinetic
PP Per-Protocol

PPI Pulmonary permeability index

PT Preferred term

P&VFD Vasopressor and mechanical ventilator free days

QALY Quality adjusted life years

RAR Response adaptive randomisation

RRT Renal replacement therapy

ScvO2 Oxygen Saturation in Vena Cava Superior SOFA Sequential Organ Failure Assessment score

Date: 20 Nov 2017 E-Statistical Analysis Plan-17877; Ver.9.0 Supersedes: Ver. 8.0

Page 11 of 80

Abbreviations Meaning of abbreviations in document

SOC System Organ Class WBC White blood cells

Page 12 of 80

2 Trial Objectives and Endpoints

2.1 Objectives

Primary Objective

• To demonstrate superiority of selepressin plus standard care versus placebo plus standard care in the number of vasopressor- and mechanical ventilator-free days (with penalty for mortality) in patients with vasopressor-dependent septic shock

Secondary Objectives

- To determine the efficacy of selepressin on:
 - Organ dysfunction
 - Morbidity and mortality
 - o Fluid balance
 - o Health-related quality of life
- To determine the safety profile of selepressin
- To determine the pharmacokinetics of selepressin
- To determine the health economics of selepressin
- To further evaluate a range of biomarkers in relation to the mode of action of selepressin

2.2 Endpoints

2.2.1 Primary Endpoint

• Vasopressor- and mechanical ventilator-free days (P&VFDs) up to day 30

2.2.2 Key Secondary Endpoints

- All-cause mortality (defined as the fraction of patients that have died, regardless of cause, by the end of Day 90)
- Renal replacement therapy (RRT)-free days up to Day 30 (excluding patients on RRT for chronic renal failure at time of randomisation)
- Intensive care unit (ICU)-free days up to Day 30

2.2.3 Secondary Endpoints

Organ dysfunction

- Vasopressor-free days up to Day 30
- Mechanical ventilator-free days up to Day 30
- Duration of septic shock up to Day 30

Page 13 of 80

- Duration of mechanical ventilation up to Day 30
- Incidence of RRT up to Day 30 (counting patients who die as on RRT and excluding patients on RRT for chronic renal failure at time of randomisation)
- Duration of RRT up to Day 90 (excluding patients on RRT for chronic renal failure at time of randomisation)
- Daily overall and individual organ (cardiovascular, respiratory, renal, hepatic, coagulation) scores using the modified Sequential Organ Failure Assessment (SOFA) scores until ICU discharge
- Incidence of new organ dysfunctions and new organ failures (based on the SOFA score) up to Days 7 and 30

Morbidity/mortality

- ICU length of stay up to Day 30
- All-cause mortality (defined as the fraction of patients that have died, regardless of cause, by the end of Days 30 and 180)

Fluid balance

- Daily and cumulative fluid balance until ICU discharge (for a maximum of 7 days)
- Daily and cumulative urinary output until ICU discharge (for a maximum of 7 days)

Health-related quality of life

• Change in utility, based on EQ-5D-5L, up to Day 180

2.2.4 Safety Endpoints

- Incidence of adverse events (type, frequency, and intensity) with specific emphasis on:
 - o Ischaemic events (e.g. myocardial, skin, cerebral, mesenteric, and limb ischaemia)
- Changes in vital signs and safety laboratory variables, including:
 - Number of clinically significant results assessed as unanticipated in the setting of septic shock
- Episodes of hypotension

2.2.5 Additional Endpoints

- Hospital-free days up to Day 90
- Hospital length of stay up to Day 90
- Patient residence at Day 30, Day 60, Day 90, and Day 180
- Mean arterial pressure (MAP), until ICU discharge (for a maximum of 7 days)

Page 14 of 80

- Norepinephrine/noradrenaline and other vasopressor doses
- Pharmacokinetic response (in a subset of approximately 200 patients) to be reported separately according to a pre-specified pharmacokinetic analysis plan
- Health economic evaluation to be reported separately according to a pre-specified health economic analytical plan
- Creatinine Clearance
- PaO2/FiO2 ratio (in a subset of 100-350 patients)
- Extravascular Lung Water and Pulmonary Permeability Index (in a subset of 100-350 patients)
- Cardiac output (in a subset of 100-350 patients)
- Cytokines (in a subset of 100-350 patients)
- Angiopoietin 1 and 2 levels (in a subset of 100-350 patients)

2.2.6 Other Assessments

- Central Venous Pressure
- Central Venous Oxygen Saturation
- Arterial Blood Gases (PaO2, PaCO2, SaO2, pH, HCO3, base excess) and Lactate

Page 15 of 80

3 Trial design

3.1 General Design Considerations

The overall adaptive design is a Phase 2b/3 trial, in which dose-ranging with response-adaptive randomization (RAR) (see Appendix 5 for details) is utilized in a first part (the Phase 2b part – Part 1), followed by a traditional 1:1 randomised comparison of selepressin to placebo in the second part (the Phase 3 part – Part 2). The final analysis uses patients from both parts of the trial. The entire trial, combining both parts, represents an adequate and well-controlled comparison of selepressin and placebo.

In Part 1 of the trial, up to four dosing regimens will be investigated.

Arm 1: Starting dose at 1.7 ng/kg/min, and a max. dose of 2.5 ng/kg/min

Arm 2: Starting dose at 2.5 ng/kg/min, and a max. dose of 3.75 ng/kg/min

Arm 3: Starting dose at 3.5 ng/kg/min, and a max. dose of 5.25 ng/kg/min

Arm 4: Starting dose at 5 ng/kg/min, and a max. dose of 7.5 ng/kg/min

Part 1 comprises a minimum of 300 evaluable patients and a maximum of 800 treated patients. During Part 1, patients will be randomised to placebo or selepressin (Arms 1 to 3). Arm 4 will only be opened between 200 evaluable- 600 treated patients and if there is at least a 50% probability that Arm 3 has a higher expected P&VFD than Arm 2 and if data from the lower dosing levels do not suggest any significant safety signals. To minimize the risk of imbalance between treatment arms, randomisation will be stratified based on trial site, the need for mechanical ventilation (Yes/No), norepinephrine/noradrenaline requirement at baseline (< or \ge 30 μ g/min) and creatinine (< or \ge 150 μ mol/L) (See Appendix 7 for details).

Part 1 will begin with a 200-patients treated "burn-in" period during which fixed randomisation across the treatment arms will be used (one-third of the patients randomised to placebo and two-ninths of the patients to each of the selepressin arms [Arms 1 to 3]). The factors described above will be used to stratify the randomisation.

After completion of the burn-in period, Part 1 will utilize response-adaptive randomisation to preferentially place patients into the arms that appear to have the maximum benefit with respect to the primary endpoint. A fixed fraction (one third) of patients will be randomised to placebo throughout Part 1 to ensure contemporaneous control patients are enrolled throughout the trial.

If Part 1 culminates in the decision to run Part 2, Part 2 will be a 1:1 comparison of placebo to the best-performing active treatment arm. The best-performing active treatment arm will be identified at the end of Part 1. Part 2 will utilize a fixed 1:1 randomisation proportion, with stratified randomisation as described for Part 1. Part 2 can begin after any interim analysis after 300 evaluable -800 treated patients in Part 1 and the size of Part 2 will include enough patients to bring the total number of evaluable patients in Part 1 and Part 2 up to 1800, ensuring a minimum sample size of Part 2 of 1000 evaluable patients.

Page 16 of 80

[figure not shown]

Figure 1: Design Flow Chart

Date: 20 Nov 2017 E-Statistical Analysis Plan-17877; Ver.9.0 Supersedes: Ver. 8.0

Page 17 of 80

3.2 Determination of Sample Size

At least 1800 evaluable patients combined for Part 1 and Part 2 are needed for the final analysis. The overall power of obtaining statistical significance based on combined evidence from Part 1 and Part 2 is 91% in situations where all 4 arms have a true underlying 1.5% lower mortality rate and a 1.5-day higher expected number of P&VFDs for survivors as compared to placebo (corresponding to an overall treatment effect of 1.5 P&VFDs). If the effect sizes are 2% on mortality and 2 days for P&VFDs in survivors for all 4 arms (corresponding to an overall treatment effect of 2 P&VFDs), then the overall power is 98%. In this latter case the probability of engaging into Part 2 is ~99%.

Date: 20 Nov 2017 E-Statistical Analysis Plan-17877; Ver.9.0 Supersedes: Ver. 8.0

Page 18 of 80

4 Patient Disposition

A summary table will present, for each part of the trial and overall, the number of patients in the population sets: 'Screened', 'Intention to treat', Full analysis set', 'Per protocol', 'Safety', 'Completed trial', 'Withdrawals', and 'IMP discontinuations' with a breakdown of reasons/categories for trial withdrawals and IMP discontinuations.

The patient disposition table will be broken down by each of the stratification variables [the need for mechanical ventilation (Yes/No), norepinephrine/noradrenaline requirement at baseline (< or \ge 30 µg/min) and creatinine (< or \ge 150 µmol/L)] and broken down chronologically displaying number of patients 'completed' and 'withdrawn from trial' at Day 30, Day 90 and Day 180.

The number of patients screened but not randomised/allocated to treatment will be presented with the reason(s) for screen failure in a data listing.

All major protocol violations (including misrandomisations), based on the Full analysis set, will be summarised for each part of the trial.

Furthermore 1-KM plots, based on the ITT, will be presented for the time to trial withdrawals/IMP discontinuations (whichever comes first) differentiated by reason of trial withdrawal/IMP discontinuation using cumulative incidence functions. Dropout rates between treatment groups will be evaluated by the log-rank test.

Date: 20 Nov 2017 E-Statistical Analysis Plan-17877; Ver.9.0

Supersedes: Ver. 8.0 Page 19 of 80

5 Protocol Deviations

Patient data in the full analysis set (FAS) will be excluded from the per-protocol (PP) analysis set if they meet any of the following criteria:

- Dosing errors expected to significantly impact efficacy
- More than 16 hours from onset of vasopressor treatment to start of IMP
- Failed to receive a continuous infusion of norepinephrine/noradrenaline base greater than 4.5 ug/min for at least one hour or received less than 4.5 ug/min of norepinephrine/noradrenaline base at start of IMP infusion
- Violation of exclusion criteria 2: Primary cause of hypotension not due to sepsis (e.g., major trauma including traumatic brain injury, hemorrhage, burns, or congestive heart failure/cardiogenic shock)
- Violation of exclusion criteria 6: Chronic mechanical ventilation for any reason OR severe chronic obstructive pulmonary disease (COPD) requiring either continuous daily oxygen use during the preceding 30 days or mechanical ventilation (for acute exacerbation of COPD) during the preceding 30 days
- Violation of exclusion criteria 9: Decision to limit full care taken before obtaining informed consent
- Violation of exclusion criteria 10: Use of vasopressin in the past 12 hours prior to start of IMP infusion or use of terlipressin within 7 days prior to start of IMP infusion
- Violation of exclusion criteria 12: Prior use of an investigational medicinal product within the last month OR planned or concurrent participation in a clinical trial for any investigational drug or investigational device

Furthermore, any other major protocol violations, such as serious unforeseen violations deemed to invalidate the data and affect the conclusions of the study will lead to exclusion of data from the PP analysis set.

Major protocol deviations will lead to exclusion of data from the PP analysis, while data will not be excluded because of minor protocol deviations. The list of major protocol deviations will be detailed and documented in the clean file document prior to database release.

All major protocol deviations will be listed in patient data listings.

Page 20 of 80

6 Analysis sets

6.1 Intention-To-Treat Analysis Set

The intention-to-treat (ITT) analysis set comprises of all randomised (as planned) patients.

6.2 Full-Analysis Set

The FAS comprises data from all randomised (as planned) and dosed patients.

6.3 Per Protocol Analysis Set

Patients in the FAS will be excluded from the PP analysis set if they meet any major protocol violations defined in (Section 5). Data will be used up to the point of protocol violation.

6.4 Safety Analysis Set

The safety analysis set comprises all treated patients and are analysed according to the actual treatment received.

Page 21 of 80

7 Trial population

7.1 Demographics and Other Baseline Characteristics

Categorical data will be summarised using numbers and percentages. The percentages are based on the total number of patients with a corresponding assessment. Continuous data will be presented, for example, using the number of patients (N), mean and standard deviation, median, interquartile range, minimum and maximum. All baseline characteristics will be listed.

Demographics and baseline characteristics of the study population will be summarised for the FAS.

7.1.1 Demographics

Descriptive statistics of baseline demographics variables will be summarized by treatment arm and total.

7.1.2 Vital Signs at Baseline

Baseline vital signs will be summarised by treatment arm and total.

7.1.3 SOFA Score, APACHE II Score and Septic Shock Characteristics

Baseline SOFA score (modified), APACHE II score and information on septic shock (infection proven/suspected, primary infection type and location will be summarised by treatment arm and total.

7.2 Medical History

Medical history recorded at screening visit will be summarised by treatment arm and total.

Furthermore, medical history will be presented in patient data listings.

7.3 Prior and Concomitant Medication

Prior and concomitant medication will be summarised by treatment arm and total.

Furthermore, concomitant medication will be presented in patient data listings.

Page 22 of 80

8 Exposure and Treatment Compliance

8.1.1 Extent of Exposure

The total amount (adjusted by weight $(\mu g/kg)$) of selepressin administered and the number of days (reported to one decimal place) treated with selepressin will be summarised by (active) treatment arm and total (active treatment arms).

Furthermore, the mean cumulative amount administered and the mean infusion rate will be tabulated by treatment arm and presented graphically (also by treatment arm and total).

If a patient has missing infusion rate and the patient is still in the trial (not dead or withdrawn) it will be assumed that selepressin was not administered and a value of zero will be imputed, unless there is an interval in the timing log covering the exact time point (8 AM and 8 PM is the assumed time point for missing morning and evening collection time points). In that case LOCF will be used, but only within the time interval.

If a patients has missing cumulative selepressin volume and the patient is still in the trial (not dead or withdrawn), LOCF will be used assuming that selepressin was not administered and hence keeping the cumulative volume constant.

Date: 20 Nov 2017 E-Statistical Analysis Plan-17877; Ver.9.0

Supersedes: Ver. 8.0 Page 23 of 80

9 Efficacy

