9.4.5 Norepinephrine/Noradrenaline and Other Vasopressor Doses

The cumulative dose of norepinephrine/noradrenaline administered (adjusted for baseline weight) will be derived as an area under the curve (AUC) of the actual norepinephrine doses and actual time points (although analysed at planned time points). Linear interpolation will be used to derive the AUC (taking into account that only patients enrolled before noon will have a measurement at 36 hours after IMP start). Patients dead or withdrawn will be set to missing. The cumulative doses ($\mu g/kg$) will be compared between treatment arms using a repeated measures ANCOVA model with baseline dose of norepinephrine/noradrenaline ($\mu g/kg/min$) as covariate, treatment, time and treatment by time interaction as factors, baseline dose by time interaction, and patient as the experimental unit. Estimated treatment differences (to placebo) along with a 95% confidence interval will be presented.

If a patient has missing values and the patient is still in the trial (not dead or withdrawn) it will be assumed that the specific vasopressor was not given and a value of zero will be imputed, unless there is an interval in the timing log covering the exact time point (8 AM and 8 PM is the assumed time point for missing morning and evening collection time points). In that case LOCF will be used, but only within the time interval.

Date: 20 Nov 2017 E-Statistical Analysis Plan-17877; Ver.9.0 Supersedes: Ver. 8.0

Page 40 of 80

The mean dose and cumulative dose administered will be tabulated by treatment arm (including pooled active treatment arms), and presented graphically.

To assess the time needed to wean the patients off norepinephrine, the percentage change from baseline in norepinephrine dose ($\mu g/kg/min$) will be compared between treatment arms using a repeated measures ANCOVA model with baseline dose of norepinephrine/noradrenaline ($\mu g/kg/min$) as covariate, treatment, time and treatment by time interaction as factors, baseline dose by time interaction, and patient as the experimental unit. Estimated treatment differences (to placebo) along with a 95% confidence interval will be presented at 1, 3, 6, 12 and 24 hours after start of IMP treatment.

The same analyses (adjusted for baseline dose of norepinephrine/noradrenaline ($\mu g/kg/min$)) will be performed for the following endpoints:

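### The missing-volume rule in Section 8.1.1 assumes no drug was given even where the timing log shows the infusion running, so cumulative selepressin is understated at those time points

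*SAP*

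**What the plan says.** SAP Section 8.1.1 gives two imputation rules, both for patients who are still in the trial.

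- **Missing infusion rate.** By default "it will be assumed that selepressin was not administered and a value of zero will be imputed". The plan lifts this default when the timing log records an infusion spanning the moment in question. For a reading inside a logged interval, "In that case LOCF will be used, but only within the time interval". Where the collection time itself is missing, "8 AM and 8 PM is the assumed time point for missing morning and evening collection time points".
- **Missing cumulative volume.** "LOCF will be used assuming that selepressin was not administered and hence keeping the cumulative volume constant". The timing log is not mentioned.

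The section reports total amount per kg and days treated. It adds that "the mean cumulative amount administered and the mean infusion rate will be tabulated by treatment arm and presented graphically". It does not say whether total amount comes from the recorded cumulative volumes or from rate multiplied by time.

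For norepinephrine and other vasopressors, Section 9.4.5 uses the same default, "it will be assumed that the specific vasopressor was not given and a value of zero will be imputed", with the same timing-log exception. Its cumulative norepinephrine dose is an area under the curve of the doses, so no separate rule for a missing cumulative value is needed.

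**The concern.** The timing log is the trial's own record of when the infusion was running, and the rate rule relies on it. The volume rule does not. For a patient whose log shows an infusion under way, it states an assumption that the log contradicts. If both readings are missing at that time, one patient is given a positive rate and no added volume for the same period. If only the volume is missing, the frozen value is still too low whenever the rate is positive.

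At stake is the accuracy of the exposure summaries. Mean cumulative amount and mean infusion rate are presented by arm from inputs imputed under incompatible assumptions, and relative to the rate rule the error in cumulative amount never goes upward.

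**Working it through.** The plan gives no figure to reproduce here. The check is a comparison of the two rules, followed by an illustration of size.

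**1. Where the rules conflict**

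| Situation, reading missing | Rate rule | Volume rule | Consistent? |
|---|---|---|---|
| No logged infusion at that time | Zero | Held constant | Yes, both mean no drug |
| Logged infusion, last rate positive | Last rate carried forward | Held constant | No |
| Logged infusion, last rate zero | Zero carried forward | Held constant | Yes |

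The conflict is confined to the second row.

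**2. Amount missed per gap**

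Inputs: starting and maximum rates from Section 3.1 (for example, "Arm 2: Starting dose at 2.5 ng/kg/min, and a max. dose of 3.75 ng/kg/min"). Assumptions: a constant rate and a 12-hour gap lying wholly inside a logged infusion. The 12 hours is the spacing between the 8 AM and 8 PM default times.

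Amount (µg/kg) = rate (ng/kg/min) × 60 × 12 / 1000 = rate × 0.72.

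| Arm | Starting rate | Missed amount | Maximum rate | Missed amount |
|---|---|---|---|---|
| 1 | 1.7 | 1.22 | 2.5 | 1.80 |
| 2 | 2.5 | 1.80 | 3.75 | 2.70 |
| 3 | 3.5 | 2.52 | 5.25 | 3.78 |
| 4 | 5 | 3.60 | 7.5 | 5.40 |

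The volume rule adds 0 in every cell. A 24-hour gap doubles these amounts.

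**3. Does the error persist?**

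Take Arm 2 at a constant 2.5 ng/kg/min, with readings every 12 hours over an assumed 48-hour infusion. Cumulative amounts in µg/kg:

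| | 0 h | 12 h | 24 h | 36 h | 48 h |
|---|---|---|---|---|---|
| Implied by log and rate | 0 | 1.8 | 3.6 | 5.4 | 7.2 |
| 24 h volume missing, rule applied | 0 | 1.8 | 1.8 | 5.4 | 7.2 |
| 48 h volume missing, rule applied | 0 | 1.8 | 3.6 | 5.4 | 5.4 |

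A missing intermediate reading halves the value at 24 hours (1.8 against 3.6), but the next recorded volume restores the total. A missing last reading leaves the total at 5.4 instead of 7.2: 1 − 5.4/7.2 = 25% too low.

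**4. Dependence on infusion length**

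With a constant rate and the last 12-hour reading missing, the proportional shortfall is 12 / total hours:

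- 24-hour infusion: 12/24 = 50%
- 48-hour infusion: 12/48 = 25%
- 7-day infusion: 12/168 = about 7%

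The rate cancels, so for the same gap and duration the proportion is the same in every arm. Only the absolute shortfall rises with the rate.

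**The case against.** The strongest defence is that the volume rule is right for what is probably its main use. Patients remain in the trial long after the infusion stops, with endpoints up to Day 180, and a blank cumulative volume then should stay constant. Outside logged intervals the two rules agree. Cumulative readings also correct themselves once a later one is recorded. All of this stands. It narrows the fault to logged infusion periods but does not remove it there.

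Three stronger readings are tempting, and the SAP does not support them.

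- **That dose received is understated in general, or that the exposure tables must disagree.** Total amount is understated only if the last volume during infusion is missing and the total is taken from volume. The SAP is silent on the source; a total built from the imputed rates would be unaffected. Mean rate and cumulative amount are also different quantities, and the SAP does not promise that they reconcile.
- **That adverse events are read against too low an exposure.** Sections 10.1 and 10.2 tabulate patients, percentages and event counts by arm. Treatment emergence depends on when the infusion starts and stops. No planned adverse event analysis uses cumulative amount. The primary endpoint likewise rests on start and stop times.
- **That exposure contrasts between arms are badly distorted.** For equal gaps and durations, ratios between arms are unchanged and only absolute differences shrink. Appendix 5 also allows that different assigned maximum doses could be titrated to a similar delivered treatment, so the nominal rates need not show the real gradient.

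It is also fair that carrying a rate across a gap in a titrated infusion is itself an imputation. It can overstate the amount where no later reading limits it.

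**Conclusion.** The rule is wrong as written, within a narrow scope. Followed exactly, Section 8.1.1 yields a cumulative amount that the timing log contradicts whenever a volume is missing during a logged infusion at a positive rate. The missing exception is the fault; carrying the volume forward after the infusion has ended is correct.

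The illustrated size is 1.22 to 5.40 µg/kg per 12-hour gap across arms and rates. If the last reading is the missing one and the total comes from volume, the total falls short by 50%, 25% or about 7% for a 24-hour, 48-hour or 7-day infusion. These figures rest on an assumed constant rate, gap length and infusion duration. The frequency of missing readings is not given, so the effect on arm means cannot be computed and could be negligible.

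The consequence is limited to descriptive exposure tables and graphs. This is a small correction worth making, not a threat to the trial's conclusions.

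**What to change.** Amend Section 8.1.1 so that the timing log governs both readings. Either of these would do:

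1. Where the log covers the gap, add the carried-forward rate multiplied by the logged infusion time to the last recorded cumulative amount, capped by the next recorded value where there is one.
2. Derive cumulative amount in µg/kg from the imputed rates, in line with the area-under-the-curve approach that Section 9.4.5 uses for norepinephrine.

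In either case, hold the cumulative amount constant only where the log shows no infusion, and state which source defines total amount. Working in µg/kg avoids converting the carried-forward rate to a volume, for which the SAP gives no concentration.

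The cost is a sentence or two in the SAP and a small change to the derivation. It uses the log and the carried-forward rate that the rate rule already relies on, so no new data collection is indicated. The downside is possible overstatement when a rate is carried to the end of an infusion with no later reading; a count of patients with an imputed last value, shown beside the table, would make this visible.
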